**TREATMENT PATTERNS AND CLINICAL OUTCOMES AMONG PATIENTS IN
LATIN AMERICA RECEIVING FIRST LINE PALBOCICLIB COMBINATIONS
FOR HORMONE RECEPTOR POSITIVE/ HUMAN EPIDERMAL GROWTH
FACTOR RECEPTOR 2 NEGATIVE (HR+/HER2-) ADVANCED/METASTATIC
BREAST CANCER IN REAL WORLD SETTINGS**

This document contains confidential information belonging to Pfizer. Except as otherwise agreed to in writing, by accepting or reviewing this document, you agree to hold this information in confidence and not copy or disclose it to others (except where required by applicable law) or use it for unauthorized purposes. In the event of any actual or suspected breach of this obligation, Pfizer must be promptly notified.

Study Information

Title	Treatment Patterns and Clinical Outcomes Among Patients in Latin America Receiving First Line Palbociclib Combinations For hormone receptor positive/ human epidermal growth factor receptor 2 negative (HR+/HER2-) Advanced/Metastatic Breast Cancer in Real World Settings.
Protocol number	A5481125
Protocol version identifier	Version 3.0
Date	13 August 2020
Date of last version of protocol	16 April 2019
Active substance	L01XE33 - Palbociclib
Medicinal product	Ibrance (palbociclib)
Research question and objectives	To describe patient demographics, clinical characteristics, treatment patterns and clinical outcomes of adult female patients who have received palbociclib combination treatments as first line therapy, regardless of combination partner and labelled use in real world settings across Latin America.
Primary objectives	
To describe demographics and clinical characteristics of patients who have received palbociclib combination treatment as a first line therapy, regardless of combination partner and labelled use.	
To describe adjuvant therapies received for the treatment of early or locally advanced breast cancer (Stages 0-IIIa).	
To describe treatments received in the advanced/metastatic setting, before and after palbociclib combination use.	
To describe dosing and dose changes, interruptions, and delays associated with palbociclib use in clinical practice.	

To detail supportive therapies received by patients while receiving palbociclib combination treatment.

To determine in overall population and defined subgroups, clinical outcomes including.

Proportion of patients who are progression free at specific intervals (eg, 6, 12, 18 months).

Objective response rate (ORR).

1. LIST OF ABBREVIATIONS

Abbreviation	Definition
ABC	Advanced Breast Cancer
AE	Adverse Events
AEM	Adverse Event Monitoring
AI	Aromatase Inhibitor
CDK	Cyclin Dependent Kinase
eCRF	Electronic Case Report Form
FDA	Food Drug Administration
GPP	Guidelines for Good Pharmacoepidemiology Practices
HER2-	Human Epidermal Growth Factor Receptor 2 Negative
HR+	Hormone receptor positive
IEC	Independent Ethics Committee
IRB	Institutional Review Board
IRIS	Ibrance Real World Insights
ISPE	International Society for Pharmacoepidemiology
MBC	Metastatic Breast Cancer
NIS	Non-Interventional Study
ORR	Objective Response Rate
PFS	Progression Free Survival
PHI	Personal Health Information
Q1	First Quarter
SAP	Statistical Analysis Plan
TPP	Time to Progression
US	United States
WIRB	Western Institutional Review Board

3. ABSTRACT

Title: Treatment Patterns and Clinical Outcomes among Patients in Latin America Receiving First Line Palbociclib Combinations for hormone receptor positive/ human epidermal growth factor receptor 2 negative (HR+/HER2-) Advanced/Metastatic Breast Cancer in Real World Settings.

Rationale and background: Breast cancer is a major cause of mortality in females worldwide. Hormone receptor positive (HR+) and human epidermal growth factor receptor 2 negative (HER2-) breast cancer is the most commonly diagnosed subtype accounting for around 74% of all diagnosed breast cancers. Palbociclib is a first in class CDK4/6 inhibitor that has been approved for use in HR+/HER- advanced/ metastatic breast cancer (ABC/ MBC) patients in several indications on the basis of efficacy demonstrated in three pivotal clinical trials; PALOMA-1 and PALOMA 2 (initial endocrine-based therapy) and PALOMA-3 (after progression following endocrine therapy). As a result of the recent approvals, there is a need to understand the real-world usage and clinical outcomes of patients receiving palbociclib at first line in order to inform future treatment decisions. The Global IRIS study has been previously conducted in the US, Canada, Germany, Belgium, UK, Italy, Spain, Switzerland, Netherlands, Japan, France, Portugal and a previous Latin American wave in Chile, Argentina, Peru, Mexico, Costa Rica, and Panama. Here we aim to replicate the IRIS study in Latin America however only focusing on palbociclib as first line therapy, regardless of combination partner or indication.

Research question and objectives: The primary objectives of this study are to describe the patient demographics, clinical characteristics, treatment patterns, and clinical outcomes of adult female patients who have received palbociclib in the first line setting to treat HR+ /HER2- ABC/ MBC. All use of palbociclib in the first line setting will be captured regardless of combination partner and labelled use.

Study design: This retrospective physician based medical record review will collect data from medical records of patients, who have received palbociclib combination therapy as first line treatment for ABC/MBC, across 7 countries in Latin America. Data collection in 6 countries has already been conducted: Chile, Argentina, Peru, Mexico, Costa Rica, and Panama. In countries where palbociclib has been on the market for a sufficient period of time and therefore sufficient follow-up data are available, a one-time review of patient's medical records will be conducted.

Population: Data will be collected from Colombia with approximately 30-40 oncologists or gynecologists recruited. To be eligible to participate physicians must have treated or be treating 4 or more HR+/HER2- ABC/MBC patients with palbociclib combination therapy in the first line setting. Each physician will complete up to 8 electronic case report forms (eCRFs). Previously data has been collected in Chile (1 oncologist providing 8 eCRFs, Argentina (41/469), Peru (5/30), Mexico (15/99) and Costa Rica (6/35) and Panama (1/6).

Recruited physicians must go back in their records to the specific index date and select the next 'n' number of eligible patients for which they will complete eCRFs. The 'index date' will be defined as 60 days after the physician first prescribed palbociclib + partner therapy following the availability of specific indication in the market. To be eligible, patients must be female, aged 18 or over, have been diagnosed with HR+/HER2- ABC/ MBC and must have received palbociclib combination as a first line therapy. They also must have a minimum of six months follow up data since palbociclib + aromatase inhibitor initiation and three months follow up data for palbociclib + fulvestrant initiation.

It is expected that approximately 30-40 physicians will be recruited in Colombia to complete 200 eCRFs, combined and with previous data collection in Chile, Argentina, Peru, Mexico, Costa Rica and Panama, it is expected that approximately 99-109 physicians will be recruited in total, this will enable data to be collected for approximately 790-890 patients overall across Latin America.

Variables: The variables assessed in this study will be patient demographics at the time of data collection, clinical characteristics, comorbid conditions, early and advanced breast cancer treatment history, palbociclib treatment patterns including dose changes, clinical outcomes and time since deceased (no. of days) if applicable.

Data sources: Patient medical records will be used as the data source.

Study size: Approximately 30-40 physicians will be recruited in Colombia collecting data for approximately 200 patients. In Argentina, Mexico, Costa Rica, Panama, Peru and Chile, 69 physicians were recruited overall, which enabled data to be collected for 647 patients. This sample is in addition to that previously collected in Argentina in wave 1 Global IRIS (162 patient records were collected from 41 physicians, protocol no. A5481090). In Mexico, 15 physicians were recruited collecting 99 eCRFs. Five physicians in Peru collected 30 eCRFs. A total of 7 physicians were recruited across Costa Rica and Panama with a sum of 41 CRFs. In Chile 1 physician was recruited collecting a total of 8 eCRFs.

Data analysis: All analyses will be descriptive in nature. Categorical variables will be described using the number of observations and number and percent (%) in each category. Numeric variables will be described using the number of observations, mean and standard deviation, and minimum, maximum, median and interquartile range. Time to event will be described using a Kaplan-Meier chart or the median.

Milestones: The medical record review data collection began in June 2019 and was completed by September 2019 for Argentina, Mexico, Costa Rica, Panama, Peru and Chile. Medical record review collection for Colombia is due to begin August 2020 and should be completed by October 2020; however this will depend upon market approval dates and the required follow-up time for outcomes evidence. Following completion of data collection in all markets, the final study report will be written and completed by December 2020.

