7. RESEARCH QUESTION AND OBJECTIVES

The primary objective of this real-world study is to describe patient demographics, clinical characteristics, treatment patterns and clinical outcomes of adult female patients who have received palbociclib combination treatments as first line therapy, regardless of combination partner and labelled use:

Argentina:

- Palbociclib in combination with letrozole as early endocrine therapy to treat advanced/metastatic HR+/HER2- post-menopausal breast cancer (ARG:14th December 2015);

- Palbociclib in combination with fulvestrant for the treatment of women with HR+/HER2- ABC/MBC with disease progression following endocrine therapy (ARG: 16th August 2016).

Chile:

- Palbociclib in combination with letrozole as initial endocrine-based therapy for the treatment of postmenopausal women with HR+/HER2- locally ABC/MBC (June 2015);
- Palbociclib in combination with fulvestrant for the treatment of woman with HR+/HER2- ABC/MBC with disease progression following endocrine therapy (June 2015).

Colombia:

- Palbociclib in combination with letrozole as initial endocrine therapy to treat advanced/metastatic HR+/HER2- ABC/MBC in post-menopausal women (November 2018);
- Palbociclib in combination with fulvestrant for the treatment of women with HR+/HER2- ABC/MBC with disease progression following prior endocrine therapy (November 2018).

Costa Rica:

- Palbociclib in combination with aromatase inhibitor for the treatment of women with HR+/HER2- locally ABC/MBC (August 2016);
- Palbociclib in combination with fulvestrant for the treatment of woman with HR+/HER2- ABC/MBC who have received prior endocrine therapy (August 2016).

Panama:

- Palbociclib in combination with aromatase inhibitor as initial endocrine based therapy in postmenopausal women with HR+/HER2- locally ABC/MBC (July 2017);
- Palbociclib in combination with fulvestrant for the treatment of women with HR+/HER2- ABC/MBC with disease progression following endocrine therapy (July 2017).

Perú:

- Palbociclib in combination with aromatase inhibitor as initial treatment with endocrine basis for post-menopausal women with HR+/HER2- locally ABC/MBC (May 2016);

- Palbociclib in combination with fulvestrant for the treatment of woman with HR+/HER2- ABC/MBC with disease progression following endocrine therapy (May 2016).

Mexico:

- Palbociclib in combination with letrozole as initial endocrine therapy in postmenopausal women with HR+/HER2- locally ABC/MBC (June 2016);

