8. RESEARCH METHODS

8.1. Study Design

This study will be conducted as a retrospective medical record review of patients who have received palbociclib combination treatments as first line treatment regardless of combination partner and labelled use. Upon completion, the study will comprise of a medical record review conducted in Argentina, Chile, Peru, Mexico, Colombia and a combined sample in Costa Rica and Panama. Data collect for Argentina, Chile, Peru, Mexico, Panama and Costa Rica were completed in September 2019, data collection for Colombia is due in August 2020. The study design is outlined in [Figure 1](#). The study design is similar to the IRIS Global study previously conducted (protocol no. A5481090).^{10,11}

Data collection will be online via electronic data capture using electronic case report form (eCRF). In Colombia eligible physicians will be invited to complete an eCRF for between 6-8 patients that meet the study criteria. Each eCRF will take around 25 minutes to complete. Patient eligibility will be confirmed by treating physicians. In order to allow for a sufficiently long observational window, treating physicians will be asked to go back to a specific point in time, the index date, and sequentially select the medical records of the next 'n' patients who meet the inclusion criteria. The 'index date' will be defined as 60 days after the physician first prescribed palbociclib + partner therapy following the availability of specific indication in the market (eg, If palbociclib + letrozole was available Dec 14, 2015 in Argentina and the physician initiated a patient on palbociclib+ letrozole the next day, the index date will be Feb 12, 2015). The index date will differ for the specific indications/combination partners if approved on different dates. Approval dates can be found in [Section 6](#).

[figure not shown]

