8.2. Setting

Upon study completion data will be collected from 7 countries. Approximately 30-40 physicians will be recruited in Colombia. Data will be collected retrospectively at a single point in time from patient medical records. To date, 6 physicians in Costa Rica, 1 in Panama, 1 in Chile, 15 in Mexico, 41 in Argentina and 5 in Peru completed eCRFs.

Screening questions/recruitment criteria will ensure the relevant physicians are selected and all other non-qualifying physicians will be excluded. In addition, a representative geographical split and private/public practice split for physicians will be sought where possible to ensure a representative sample.

To be eligible, physicians must have treated or be treating four or more HR+/HER2- ABC/MBC patients who meet the eligibility criteria for the study. This will ensure that recruited physicians will be able to complete the minimum number of eCRFs required to participate in the study. Once physicians have been recruited, they must go back to a specific index date, defined in [Section 7.1](#), and select the next 'n' number of eligible patient records from patients who have been treated with a palbociclib combination. The consecutive approach to recruitment will be stressed to each participating physician to limit selection bias. Physicians will confirm patient eligibility.

Patient records must meet the following criteria to be eligible for the medical record reviews. They must be female, over 18 years of age and they must have been diagnosed with HR+/HER2- ABC/MBC. Patients must have received palbociclib as a first line therapy. For the chart review, palbociclib and letrozole/aromatase inhibitor must have been initiated a minimum of 6 months prior to date of medical chart review, and palbociclib and fulvestrant must have been initiated a minimum of 3 months prior to date of medical chart review. This will permit the capture of meaningful clinical outcomes data.

A full list of the eligibility criteria can be found in [Section 8.2.1](#).

In order to ensure that sufficient data is captured for each indication, indication quotas will be enforced. This will be determined on a country by country basis.

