8.3. Variables

Table 1. List of Study Variables

Variable	Role	Data Source(s)	Operational Definition
Patient demographics	Baseline Sub-group identifier	Patient records	Age, ethnicity, weight, height, biomarker status, family history of breast cancer.
Clinical characteristics	Baseline Sub-group identifier	Patient records	Time since diagnosis, staging, node status, menopause status. ECOG/Karnofsky functional status, diagnosis for which palbociclib combination was prescribed, sites of metastases, de novo vs. recurrent disease.
Comorbid conditions	Baseline	Patient records	Comorbid conditions.
Early treatment history	Baseline Sub-group identifier	Patient records	Adjuvant treatments received since breast cancer diagnosis. Time since end of adjuvant treatment. Surgery/radiotherapy received.

Variable	Role	Data Source(s)	Operational Definition
Advanced treatment history	Baseline Sub-group identifier	Patient records	Treatments and supportive therapies received since metastatic/advanced HR+/HER2- diagnosis. Duration of treatments. Reasons for regimen changes.
Palbociclib combination treatment	Exposure Sub-group identifier	Patient records	Starting dose, duration of treatment, changes in dose, interruptions, cycle delays and discontinuations. Where possible reasons for change in treatment.
Clinical outcomes	Outcomes	Patient records	Proportion progression free, ORR, TTP, PFS, 1-yr and 2-yr survival in all patients and within specific subgroups.

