8.8. SUBGROUP ANALYSIS

Exploratory stratifications will be conducted to explore differences between, demographics, treatments, clinical characteristics, baseline co-morbidities or 'responders' and 'non-responders' to treatment, however these will be only descriptive in nature.

Responders and non-responders will be defined according to the best recorded response to palbociclib treatment.

Sample size permitting, additional stratifications may include:

- Analysis by country.

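### The abstract dates demographics to data collection, but Table 1 uses them as baseline and subgroup variables, so age and weight, recorded as written, are post-initiation values

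*Combined protocol and SAP*

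**What the plan says.** The Variables paragraph of the abstract (Section 3) is the only place that gives demographics a time point: "The variables assessed in this study will be patient demographics at the time of data collection". The same sentence lists time since death among the variables.

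Table 1 in Section 8.3 defines the demographics group as "Age, ethnicity, weight, height, biomarker status, family history of breast cancer" and assigns it the role "Baseline Sub-group identifier". It gives no measurement time.

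Section 8.8 uses the group again: "Exploratory stratifications will be conducted to explore differences between, demographics, treatments, clinical characteristics, baseline co-morbidities". The outcomes row of Table 1 also plans results within subgroups.

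Section 8.2 says how the data arise: "Data will be collected retrospectively at a single point in time from patient medical records". Sections 8.2 and 8.2.1 require at least 3 months since initiation for palbociclib with fulvestrant and at least 6 months with letrozole or another aromatase inhibitor. Under Section 8.1, physicians select patients forward from an index date that is "60 days after the physician first prescribed palbociclib + partner therapy following the availability of specific indication in the market".

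**The concern.** A baseline variable should describe the patient at, or just before, the start of the treatment being studied. The abstract fixes a different moment, the chart review, and the design guarantees that the review comes months to years later. The two statements cannot both hold for a variable that changes with time.

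This matters because the first primary objective (Section 7.1) is to describe the demographic and clinical characteristics of these patients. In a study without hypotheses, that table is itself a primary result. A reader will take a column marked baseline to mean the age and weight at which patients began first-line palbociclib. The lag also varies by country, so country-level demographic tables, and the cross-market comparisons that Section 8.1 presents as a strength, would mix real differences with differences in the time of measurement.

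**Working it through.** No lag figure stands in the protocol, so there is none to reproduce. The check is date arithmetic.

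**Inputs.** Availability dates are from Section 7 (for Argentina letrozole, "post-menopausal breast cancer (ARG:14th December 2015"). The 60-day rule is from Section 8.1. Collection in the first six countries ended on 30 September 2019 (Section 5). Colombia is planned to end in October 2020, and I assume 31 October. Record counts are from the abstract and Table 2.

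**Formula.** Maximum lag = (end of collection − [first prescription + 60 days]) / 365.25, assuming the first prescription fell on the availability date and selected patients started on or after the index date. Where only a month is given, its first and last days give the range.

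| Country | Available | Earliest index date | Maximum lag (years) | Records |
|---|---|---|---|---|
| Chile | June 2015 | 31 Jul to 29 Aug 2015 | 4.09–4.17 | 8 |
| Argentina, letrozole | 14 Dec 2015 | 12 Feb 2016 | 3.63 | 469 (both partners) |
| Argentina, fulvestrant | 16 Aug 2016 | 15 Oct 2016 | 2.96 | as above |
| Peru | May 2016 | 30 Jun to 30 Jul 2016 | 3.17–3.25 | 30 |
| Mexico | June 2016 | 31 Jul to 29 Aug 2016 | 3.09–3.16 | 99 |
| Costa Rica | Aug 2016 | 30 Sep to 30 Oct 2016 | 2.92–3.00 | 35 |
| Panama | July 2017 | 30 Aug to 29 Sep 2017 | 2.00–2.08 | 6 |
| Colombia | Nov 2018 | 31 Dec 2018 to 29 Jan 2019 | 1.75–1.83 | about 200 planned |

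Worked line for Argentina letrozole: 12 February 2016 to 30 September 2019 is 1,326 days, and 1,326 / 365.25 = 3.63 years. The example in Section 8.1 prints the index date as 12 February 2015, which precedes the availability date. The rule gives 12 February 2016, or 13 February if the first prescription was a day after availability, and I use the rule. Argentina supplies 469 / 647 = 72% of the completed records.

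**Minimum lag.** 0.25 years (fulvestrant) or 0.5 years (aromatase inhibitor), by eligibility. No patient has a lag of zero.

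**Effect on age.** For each living patient, age at review minus age at initiation equals the lag, so the mean shift equals the mean lag. The lag distribution is not in the protocol. If it is taken as uniform between a and b, the mean is (a + b)/2:

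- Colombia-like, 0.25 to 1.8 years: (0.25 + 1.8)/2 = 1.03 years.
- Argentina-like, 0.5 to 3.6 years: (0.5 + 3.6)/2 = 2.05 years.

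The direction does not depend on the assumption.

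**Other variables in the group.** Ethnicity and family history do not depend on treatment timing, and adult height hardly changes. Weight can change with disease course and treatment, but the protocol gives nothing from which to compute by how much. The date of the biomarker test is unspecified. For a patient who died before review, no value at data collection exists, and the protocol does not say what is recorded instead.

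**The case against.** The strongest reply is that one clause in the abstract is being read as an operational definition, against a body table that says baseline. Section 8.7 defers detailed methods to a separate SAP, and the eCRF is not reproduced, so the values may in fact have been captured at initiation. This stands as a limit: the protocol shows what is stated, not what was recorded. It does not remove the conflict, because the abstract clause is the only timing rule given.

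A second reply is that Section 7.1 speaks of patients who have received palbociclib, not of patients at treatment start, and that the stratifications are exploratory and descriptive. That is correct, and it limits the consequence. The role that Table 1 assigns is still baseline, and a descriptive table can still describe the wrong moment.

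A third reply is that few variables are affected. This largely stands. Age can be corrected if the dates are held, and weight is the main variable left that plainly varies with time. HR+/HER2- status is an eligibility criterion, so that part of biomarker status does not vary in this population.

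Finally, re-timing Colombia alone could make its records differ from the earlier 647. This is a real cost and is taken up in the fix.

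**Conclusion.** The inconsistency is real: the stated time point conflicts with the stated role. Every review falls at least 3 or 6 months after initiation. The maximum lag is about 3.6 years for Argentina letrozole, about 4.1 to 4.2 years for Chile (8 records only) and about 1.8 years for Colombia. These maxima assume prescribing from the availability date; later starts shorten them. Followed as written, the rule overstates age at initiation by a mean of roughly 1 to 2 years under the assumed uniform lags. Weight may be a post-treatment value, and the entry for deceased patients is undefined. There is no effect on power or type I error.

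Four stronger readings are tempting, and the documents do not support them:

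- That 3.6 years is the study-wide maximum. It is the Argentina letrozole figure, and Chile's is longer.
- That biomarker status is known to be measured late. Its timing is simply not stated.
- That a given share of patients would change age group. No age cut-point or age distribution appears in the protocol, so any such percentage would rest wholly on assumption.
- That outcome estimates in subgroups are shown to be biased. No stratum by weight or biomarker status is specified, and the eCRF wording cannot be seen.

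**What to change.** In the abstract and in Table 1, define baseline demographics (age, weight and biomarker status) as the value at, or the last recorded before, palbociclib initiation, and word the Colombia eCRF to match. Section 5 shows no actual start date for Colombia in this version, so the change can still reach the roughly 200 planned records. The same definition settles what to enter for patients who have died.

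For the 647 completed records, derive age at initiation where the dates held allow it; the protocol does not show which dates were kept, so this needs checking first. Where no value at or before initiation exists, label the value as measured at data collection, and do not use time-varying ones as baseline subgroup identifiers. If the eCRF already asked for values at initiation, correcting the abstract and adding the time point to Table 1 is enough.

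The cost is small: one sentence in the abstract, a time point in Table 1, eCRF wording for one country and a derived age variable. The drawback is that weight or biomarker status at initiation may be missing for completed records. Colombia and the earlier countries may then not be directly comparable on those variables, and should be reported separately for them.
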